Our group recently found that microRNA which are highly enriched in skeletal muscle (i.e., myomiR) are sensitive to differing exercise modes with or without essential amino acid plus carbohydrate supplementation (unpublished data). In this investigation we found that weighted endurance-type exercise diminished miR-1-3p, miR-206, miR-208a-5p, and miR-499 expression, while conventional cycle ergometry endurance exercise increased microRNA expression. However, when cycle ergometry was combined with ingestion of essential amino acids plus carbohydrate, microRNA expression was either downregulated or remained the same immediately post and during the recovery phase, compared to baseline values. Divergent microRNA were all identified to target insulin signaling, with miR-206, miR-208-5p, and miR-499 were all predicted to target Akt, an intermediate signaling protein between IRS1 and AS160. These findings suggest that diminished microRNA expression immediately following exercise may have a functional role in mediating glucose uptake to replenish glycogen stores. Corroborating our findings, previous investigations have reported the microRNA acutely altered by exercise. Following an acute bout of endurance exercise there is diminished expression of miR-23, while mRNA expression of PGC-1 α and its downstream targets are upregulated (23, 24). When miR-23 is overexpressed in skeletal muscle there is a reduction in total PGC-1 α mRNA and protein content that results in reduced efficiency of mitochondrial function, an organelle crucial to cellular energy production (23). Furthermore, endurance exercise also downregulates miR-494, another inhibitor of PGC-1 α , allowing for increased gene expression of PGC-1 α and mitochondrial transcription factor A (25). While interventions have been conducted examining the relationship of microRNA expression to energy sensing genes in response to endurance exercise, no study has investigated the influence of altered glycogen availability in response to dietary manipulation on microRNA expression. Understanding how glycogen availability alters expression of microRNA will enable determination of their functional role in regulating carbohydrate metabolism to support energy availability to fuel physical performance.

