
B3. MILITARY RELEVANCE

Military personnel often engage in sustained physical activity while time to eat and availability of food is limited (4, 36, 37). Under such conditions, it is likely that skeletal muscle glycogen stores are depleted, reducing the service member's ability to maintain an optimal level of physical performance. However, during 'real-world' military training operations there is limited knowledge regarding altered carbohydrate metabolism at the skeletal muscle level, as invasive investigations requiring muscle biopsies cannot be conducted during training operations. Identifying the mechanism, as well as determination of non-invasive markers of molecular pathways regulating carbohydrate metabolism is critical to move findings from controlled laboratory settings to field operations. Modeling of circulating microRNA may allow for a more comprehensive understanding of nutrient adequacy during military operations, allowing for implementation of targeted nutrition interventions to optimize military performance. Support for this protocol comes from Defense Health Program (DHP) Research funds, under Joint Program Committee-5 Nutrition and dietary supplements working group.

B4. OBJECTIVES/SPECIFIC AIMS/RESEARCH QUESTIONS

Objectives

1. Determine the influence of carbohydrate availability (e.g., glycogen depletion and repletion) on skeletal muscle microRNA expression, and if changes in circulating microRNA are reflective of changes in skeletal muscle microRNA.

1 2. Determine how initiation of exercise with adequate or low glycogen stores effects exogenous
2 carbohydrate efficiency.

3

4 **Hypotheses**

5

6 1. Expression of microRNA in skeletal muscle will be influenced by alterations in glycogen status, and
7 that these changes in skeletal muscle microRNA will be associated with modulation in circulating
8 microRNA.

9

10 2. Exogenous carbohydrate efficiency will be greater when exercise is initiated with lower glycogen
11 stores. Increased efficiency will be associated with higher phosphorylation of IRS-1 and AMPK.

12 **B5. RESEARCH PLAN**

13

14 **B5.1 Research Design**

15 This study will be a randomized cross-over placebo control trial.

16

17 **B5.2 Research Subjects/Population(s)**

18

19 **B5.2.1 Subject Population(s)**

20 Subject population will be representative of active duty male and female service members, being in good
21 health and recreationally active.

22

23 **B5.2.2 Number of Subjects, Records, and/or Specimens**

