- 19
- 20
- 21
- 22
- 23
- 24
- 25
- 26
- 27
- 28
- 29
- 30
- 31
- 32
- 33
- 34
- 35
- 36
- 37
- 38
- 39
- 40
- 41
- 42
- 43
- 44
- 45
- 46
- 47
- 48
- 49
- 50

B5.3 Research Procedures

Study Design

Following a 10-hr overnight fast, a baseline blood draw will be conducted. A baseline muscle biopsy, obtained from the lateral portion of the vastus lateralis, will be collected under local anesthetic (lidocaine). Participants will rest for 15-min before beginning a 5-min warm-up on a cycle ergometer at 50% peak power output (determined from screening $VO_{2\text{peak}}$ test). A glycogen depletion protocol (38) will then be initiated with participants cycling at various intensities until failure. A second muscle biopsy will be performed immediately after completion of glycogen depletion. This biopsy will allow for confirmation of glycogen depletion and allow for the assessment of the initial impact of exercise-induced glycogen depletion on microRNA expression. Participants will then consume a carbohydrate (CHO: $1 \text{ g}\cdot\text{kg}^{-1}\cdot\text{hr}^{-1}$) or an energy free control (CON) beverage matched for taste and color during the first 3-hr post glycogen depletion. Blood will be drawn from a catheter every 30-min post-exercise to assess changes in serum glucose and insulin. At 3-hr post-exercise a third muscle biopsy will be conducted to assess acute effects of carbohydrate consumption on microRNA during the initial phase of glycogen resynthesis during the early phase recovery from exercise. For the remainder of the day participants will consume meals ready-to-eat (MRE) components designed to adequately or inadequately replenish glycogen stores. On the study day in which participants receive the carbohydrate beverage, daily intake will be provided as $6.0 \text{ g}\cdot\text{kg}^{-1}$ carbohydrate, $1.2 \text{ g}\cdot\text{kg}^{-1}$ protein, $1 \text{ g}\cdot\text{kg}^{-1}$ fat. On the study day in which participants receive the placebo beverage, daily intake will be provided as $1.5 \text{ g}\cdot\text{kg}^{-1}$ carbohydrate, $1.2 \text{ g}\cdot\text{kg}^{-1}$ protein, $3.0 \text{ g}\cdot\text{kg}^{-1}$ fat. Following a 10-hr overnight fast, participants will return to the laboratory for a fourth muscle biopsy. As 24-hrs is sufficient time to replenish glycogen stores (1), the fourth muscle biopsy with modified daily carbohydrate intake will allow for isolation of the effect of carbohydrate availability on microRNA expression. Volunteers will then complete 80-min of steady-state ($\sim 60\%$ $VO_{2\text{peak}}$) cycle ergometry consuming carbohydrate at a rate of $1.8 \text{ g}\cdot\text{min}^{-1}$ enriched with U- ^{13}C -glucose and U- $^{13}\text{C}_6$ -D-fuctose to determine exogenous carbohydrate efficiency. A final biopsy will be taken at the conclusion of the exercise bout. This fifth biopsy will be conducted to assess the impact of initiating steady-state exercise with adequate or low glycogen stores on molecular markers of glucose uptake and substrate utilization. Following a minimum 7-d washout period volunteers will return to the laboratory to complete the second arm of the investigation. To ensure glycogen stores are similar between volunteers on testing day, 48-hrs prior to testing all volunteers will complete a glycogen depletion protocol and then consume a diet providing $6.0 \text{ g}\cdot\text{kg}^{-1}$ carbohydrate to replenish glycogen stores.

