34 (Polar Electro Inc, Oulu, Finland) the last 30 seconds of each workload. The test will be stopped
35 immediately if the subject reports angina-like symptoms, exertional syncope, shows signs of poor perfusion
36 (i.e., light-headedness, confusion, ataxia, pallor, cyanosis, nausea, or cold and clammy skin), or if testing
37 equipment fails.38
39 *Glycogen Depletion Protocol*40 The glycogen depletion protocol will be completed on a cycle ergometer, with intensity based on results
41 from $\text{VO}_{2\text{peak}}$ assessment. Volunteers will begin with a 5-min warm-up at 70 watts before beginning the
42 glycogen depletion protocol. After the warm-up period volunteers will complete 2-min of high-intensity

1 cycling (work period) at 90% $VO_{2\text{peak}}$, followed by 2-min recovery period where volunteers will cycle at 50%
2 $VO_{2\text{peak}}$. This work-to-recovery ratio will be maintained until volunteers are no longer able to complete 2-
3 min of cycling at 90% $VO_{2\text{peak}}$, determined as the inability to maintain a cycling cadence of 60 rpm for 15-
4 sec. Cycling intensity will then be lowered to 80% $VO_{2\text{peak}}$. When the volunteer is unable to complete 2-
5 min of cycling at 80% $VO_{2\text{peak}}$, cycling intensity will be lowered to 70% $VO_{2\text{peak}}$. Once the volunteer can no
6 longer complete 2-min of cycling at 70% $VO_{2\text{peak}}$, cycling intensity will be lowered to 60% $VO_{2\text{peak}}$. The
7 glycogen depletion protocol will be terminated once the volunteer is unable to complete 2-min of cycling at
8 60% $VO_{2\text{peak}}$. For each drop in the intensity of the work period, the cycling intensity during the recovery
9 period will be maintained at 50% $VO_{2\text{peak}}$ for 2-min. This exercise protocol will maximally deplete muscle
10 glycogen stores (38). Prior to the protocol day, volunteers will perform two practice sessions to ensure
11 they are familiar with the glycogen depletion protocol procedures. Following familiarization volunteers will
12 complete four glycogen depletion protocols, two 48-hrs before testing and two testing days.
13

14 Volunteers will be allowed to consume water *ad libitum* during the glycogen depletion protocol. Exercise
15 will be conducted in a temperature controlled room. Heart rate will be monitored using a heart-rate monitor
16 and the session will be terminated if the subject reports any discomfort (i.e. angina-like symptoms or

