Following identification of skeletal muscle microRNA that had a significant change, Taqman® probes (Applied Biosystems) will be used to assess the expression of these microRNA in serum to determine their potential use as noninvasive markers of altered carbohydrate metabolism following glycogen depletion and repletion. Total circulating miRNA will be extracted from 200 μ L serum using miRNeasy Serum/Plasma kit, which allows for extraction and purification of small (< 200 nt) cell-free RNA (Qiagen, Valencia, CA, USA). Exosomal circulating miRNA will also be extract from 1000 μ L serum using miRCURY™ RNA Isolation Kit to measure miRNA. To avoid introduction of potentially contaminating material, prior to RNA extraction serum samples will be centrifuged for 10 min at 4°C to remove cellular debris. Supernatant will be removed and transferred to a new tube without disturbing the pellet. Due to the small amount of RNA in the serum, 3.5 μ L of a Spike-In Control (C. elegans miR-39; Qiagen) will be added to all samples prior to extraction of RNA to determine the yield of template recovered. After extraction 3 μ L of serum RNA will be reverse transcribed using the TaqMan® microRNA RT kit (Applied Biosystems) with miRNA-specific stem-loop RT primers pooled in 1X-Tris-EDTA (TE) buffer for a final dilution of 0.05X. A pre-amplification step will be performed after reverse transcription to increase cDNA template using a primer pool of 20 X Taqman® Small RNA Assays (Applied Biosystems) for miRNA of interest at 0.05X concentration in 1X TE buffer. All serum miRNA will be normalized to the geometric of external (Spike-In Control C. elegans miR-39) and internal controls to allow for both technical and inter-individual normalization (47). Geometric mean of controls will be used to correct for possible outlying values and abundance differences between the different controls (48).

All reverse transcription for mRNA and miRNA, and pre-amplification of serum miRNA will be conducted in a T100™ Thermal Cycler (Bio-Rad, Hercules, CA). A StepOnePlus™ real-time PCR system (Applied Biosystems) will be used to perform all mRNA and miRNA analysis. Fold changes will be calculated using the $\Delta\Delta C_T$ method as described below in statistical analysis section.

Bioinformatics Analysis

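### The baseline-to-post microRNA change combines exhaustive exercise with glycogen loss, and the serum marker step does not require an arm difference before linking a microRNA to carbohydrate metabolism

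*Combined protocol and SAP*

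**What the plan says.** Objective 1 in B4 begins "Determine the influence of carbohydrate availability (e.g., glycogen depletion and repletion) on skeletal muscle microRNA expression" and then asks whether circulating microRNA reflect the muscle changes.

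The Study Design text in B5.3 sets the order of events. Baseline blood and biopsy come first, then the ride to failure. Then: "A second muscle biopsy will be performed immediately after completion of glycogen depletion". That biopsy is to confirm depletion and to "allow for the assessment of the initial impact of exercise-induced glycogen depletion on microRNA expression". Only afterwards does the volunteer receive the carbohydrate or energy-free drink. The same section says that "the fourth muscle biopsy with modified daily carbohydrate intake will allow for isolation of the effect of carbohydrate availability on microRNA expression".

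The Glycogen Depletion Protocol subsection has every volunteer "complete four glycogen depletion protocols, two 48-hrs before testing and two testing days". No session is resting, uses non-depleting exercise, or lowers glycogen without exercise.

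B5.8.2 plans a repeated-measures model with main effects of time (baseline, immediately post, 3 hr, 24 hr) and of carbohydrate intake, and their interaction. B5.4 (mRNA and microRNA Expression) takes muscle microRNAs that change significantly, without saying which effect must be significant, and assays them in serum "to determine their potential use as noninvasive markers of altered carbohydrate metabolism following glycogen depletion and repletion".

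B2 reports, from the group's own data, that "conventional cycle ergometry endurance exercise increased microRNA expression".

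**The concern.** The phrase in B5.3 invites the reader to credit the baseline-to-post change to glycogen depletion, and Objective 1 names depletion as one of its two examples of carbohydrate availability. Exercise alone is a rival explanation that the protocol itself documents in B2. Nothing at the second biopsy holds exercise constant while glycogen varies.

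This matters most at the marker step. B2 and B3 give the purpose as a non-invasive signal of nutritional status in personnel on operations. Such personnel exercise whether or not they are fed. A microRNA that responds only to the ride would not tell the two situations apart, yet the selection rule as written has nothing to screen it out.

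**Working it through.** **1. The plan's own figure.** B5.8.1 gives 9 per group for a fold change of 1.5 ± 1, alpha 0.05 and 80% power. A two-sample t calculation with difference 1.5, SD 1 and two-sided 0.05 gives n = 8.06, rounded up to 9 (power 84.8%). The figure reproduces. The present point does not depend on it.

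**2. What differs at each biopsy (B5.3, Table 1).**

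| Biopsy | Exercise history | Carbohydrate difference between arms |
|---|---|---|
| Baseline | same | none |
| Immediately post | same ride to failure | none |
| 3 hr | same | carbohydrate versus energy-free drink |
| 24 hr | same | 6.0 versus 1.5 g/kg/d intake |

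**3. Can exercise and depletion be separated at the second biopsy?** Write the mean as μ + β × (exercise) + γ × (depletion).
- Baseline, either arm: exercise = 0, depletion = 0, mean = μ.
- Immediately post, either arm: exercise = 1, depletion = 1, mean = μ + β + γ.

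The two indicators are identical in all four arm-by-time cells. The design matrix has rank 2 for 3 parameters, so only the sum β + γ can be estimated, whatever the sample size.

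**4. How easily would a microRNA with no carbohydrate effect meet the rule?** The documents give no exercise effect size in these units, so the values below are assumptions shown as a range.

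(a) One-period paired t-test of the baseline-to-post change, n = 12, two-sided, with d the mean change divided by the SD of change:
- unadjusted alpha 0.05: power 0.658 at d = 0.75, 0.883 at d = 1.0, 0.975 at d = 1.25;
- four time points give 4 × 3 / 2 = 6 pairs; at alpha 0.05/6 = 0.0083, power at d = 1.0 is 0.61. Using six pairs is an assumption, since B5.8.2 says alpha will be adjusted without defining the family.

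(b) Simulation of the planned two-arm, four-time-point analysis, n = 12, 4,000 runs per row. Assumptions: no carbohydrate effect; an exercise shift present immediately post and at 3 hr and gone by 24 hr; SD of change 1; between-subject SD 0.5; no multiplicity adjustment. Entries are the share of runs significant at 0.05.

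| Shift (SD) | Time effect | Baseline-to-post, both periods averaged | Time-by-carbohydrate |
|---|---|---|---|
| 0 | 5% | 5% | 5% |
| 0.5 | 78% | 60% | 5% |
| 1.0 | 100% | 99% | 6% |
| 1.5 | 100% | 100% | 5% |

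A rule met by any significant change usually admits such a microRNA once the shift reaches 0.5 SD. A rule based on the interaction holds it near the nominal 5%.

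**The case against.** The case on the other side is substantial.

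- *The wording names a combined stimulus.* B5.3 speaks of depletion induced by exercise, and the B1 abstract does likewise. Neither claims to separate the two. This stands as a reading of those sentences, but Objective 1, Hypothesis 1 and the marker step do not carry the qualification.
- *The plan already assigns the inference sensibly.* B5.3 reserves isolation of the carbohydrate effect for the fourth biopsy, and B5.8.2 already tests carbohydrate intake and its interaction with time. This stands. A reader might infer that Objective 1 as a whole cannot be answered. The documents do not support that: at 24 hr a low-carbohydrate arm, designed to keep glycogen below baseline, is compared with a repleted arm after the same ride.
- *The marker step is exploratory.* A reader might infer that exercise-only microRNAs would be reported as field markers. B5.4 speaks only of potential use, and Objective 1 gives a good reason to assay time-responsive microRNAs in serum. Carried forward and labelled as candidates is as far as the text goes.
- *B2 is not one-sided.* Its next sentence reports that cycling with amino acids plus carbohydrate lowered expression or left it unchanged, so nutrition may modify the response. That makes the between-arm test more important. It does not separate the effects at the second biopsy.
- *Glycogen is measured, and regression is planned.* Measured glycogen confirms depletion. No model relating it to microRNA change is specified, and because the ride goes to failure, work done and depletion are likely to vary together.
- *The 88% is not the planned test.* Correct: it is unadjusted and uses one period. It shows how easily the rule could be met and does not measure harm.

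**Conclusion.** The point holds within limits. The baseline-to-post change, and any main effect of time that it drives, estimates exercise and glycogen loss together and cannot be attributed to depletion alone. This follows from the design and needs no assumption about effect size. The randomised 3-hr and 24-hr contrasts remain sound for carbohydrate availability after identical exercise.

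The practical gap is that the serum marker step is not tied to those contrasts. How often this matters depends on unknown exercise effects. Under the assumptions shown, a 1 SD response with no carbohydrate effect is significant in 61% (Bonferroni over six pairs) to 88% (unadjusted) of one-period paired tests, against about 5 to 6% for the interaction.

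Two tempting steps should be avoided. A microRNA with a time effect and no significant interaction should not be called exercise-responsive, because its change is still exercise plus glycogen loss. Nor should it be said to change equally in both arms, because non-significance in 12 people does not show equality. The arm contrast is also not carbohydrate alone: fat intake is 1.0 versus 3.0 g/kg, and the control drink has no energy.

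**What to change.** - **B4 and B5.3:** describe the baseline-to-post change as the combined response to exhaustive, glycogen-depleting exercise.
- **B5.4, marker step:** keep the serum assays of time-responsive microRNAs for the muscle-serum comparison. Call a microRNA a candidate carbohydrate marker only if it shows a time-by-carbohydrate interaction, or a multiplicity-adjusted difference between arms at the 3-hr or 24-hr biopsy. Support the claim with the within-person arm difference in measured muscle glycogen.
- **Reporting:** describe microRNAs with a time effect but no demonstrated arm difference as responsive to the combined exercise and depletion stimulus, without claiming that the arms are equal. State that the arms also differ in fat intake and in the energy content of the drink.

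The cost is wording only. The interaction test is already planned, and no samples, visits or procedures change. The downside is a shorter list of candidate markers.

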24 To complete testing on the 12 volunteers necessary to reach statistical power, we estimate we will need to
25 consent 44 individuals. All screening will stop once complete data has been collected on 12 volunteers.
26 Records and specimen collection are described in the Research Procedures and Data Collection sections.
27 During briefings and consenting potential participants will be informed that even though they may be
28 eligible and want to participate, if we are able to obtain enough data from preceding subjects, they may not
29 ultimately be tested.

30 **B5.2.3 Inclusion Criteria**

31 • Men and women aged 18 – 39 years
32 • Weight stable (± 5 lbs) for at least 2 months prior to the start of the study
33 • Body mass index (BMI) between 18.5-30 kg/m²
34 • Recreationally active based on assessment of physical activity history 2-4 days per week aerobic
35 and/or resistance exercise
36 • Refrain from taking any NSAIDS (i.e., aspirin, Advil®, Aleve®, Naprosyn®, or any aspirin-containing
37 product for 10 days before and at least 5 days AFTER each muscle biopsy. (*Tylenol® or
38 acetaminophen is ok to use if needed for discomfort)
39 • Refrain from the use of alcohol and nicotine for the duration of the study
40 • Females must be on contraception (e.g., oral birth control, NuvaRing®, Depo Provera®, etc.)
41 • Supervisor approved leave status for federal civilian employees working within the US Army Natick
42 Soldier Systems Center

[figure not shown]
43 **B5.2.4 Exclusion Criteria**

- 1 • Metabolic or cardiovascular abnormalities, gastrointestinal disorders (i.e., kidney disease, diabetes, cardiovascular disease, etc.)
- 2 • Disease or medication (i.e., diabetes medications, statins, corticosteroids, etc) that affects macronutrient utilization and/or the ability to participate in strenuous exercise
- 3 • Allergies or intolerance to foods (including but not limited to lactose intolerance/milk allergy), vegetarian practices, or medications (including, but not limited to, lidocaine or phenylalanine) to be utilized in the study
- 4 • Anemia (HCT < 38) and Sickle Cell Anemia/Trait
- 5 • Abnormal PT/PTT test or problems with blood clotting
- 6 • Present condition of alcoholism, use of nutritional/sports supplements, anabolic steroids, or other substance abuse issues
- 7 • Musculoskeletal injuries that compromise the ability to exercise
- 8 • Blood donation within 8 weeks of beginning the study
- 9 • Pregnancy
- 10
- 11
- 12
- 13
- 14
- 15
- 16
- 17
- 18

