
1
2**Figure 1. Study Design****Figure Legend:**

BL	= Baseline	*	= Blood Draw
CHO	= Carbohydrate		= Steady-state (60% VO2peak) exercise
CON	= Control		= ¹³ C-glucose / ¹³ C ₆ -D-fructose
	= Glycogen Depletion		= Resting
	= Carbohydrate or control drink		
†	= Muscle Biopsy		

3

4

5

6

Research Procedures**Diet Intervention**

Volunteers will complete a baseline 3-d diet record (**Appendix A**) and a 3-d activity log (**Appendix B**) according to instructions provided by study team dietitians (39). The data will be analyzed using Food Processor SQL™ (Salem, OR Version 10.0) and the American College of Sports Medicine (ACSM) Compendium of Physical Activities, respectively. Information for these forms will be collected to estimate volunteers total daily energy requirements. To ensure all volunteers begin the protocol day with similar glycogen stores, following glycogen depletion 48-hrs before testing, volunteers will be provided with food and beverages (except water) containing 6.0 g carbohydrate ·kg⁻¹·d⁻¹ to replete glycogen stores. Meals will be derived from military combat rations (MRE) and supplemental food items. Example of energy and macronutrient content will be consistent with ACSM dietary guidelines (**Table 1**) (40).

17

18

19

20

21

22

23

24

25

26

27

28

29

30

On glycogen depletion protocol days, volunteers will receive standardized meals derived from MRE components and supplemental carbohydrate-based food items. Meals will either provide adequate carbohydrate (6.0 g·kg⁻¹·d⁻¹) to replenish glycogen stores or provide low carbohydrate (1.5 g·kg⁻¹·d⁻¹) so glycogen stores remain below baseline concentrations (**Table 1**). Study dietitians will prepare and administer meals to volunteers. In this cross-over study the order of carbohydrate intake amount will be randomized to avoid order bias.

1 **Table 1.** Energy and Macronutrient Intake for Lead-in Diet and Protocol Days

	Lead in Diet	Protocol Days	
		Adequate CHO	Low CHO
Energy (kcal·d ⁻¹)	3024	3024	3024
Protein (g·kg ⁻¹ ·d ⁻¹ , kcal·d ⁻¹)	1.2 (384)	1.2 (384)	1.2 (384)
Carbohydrate (g·kg ⁻¹ ·d ⁻¹ , kcal·d ⁻¹)	6.0 (1,920)	6.0 (1,920)	1.5 (480)
Fat (g·kg ⁻¹ ·d ⁻¹ , kcal·d ⁻¹)	1.0 (720)	1.0 (720)	3.0 (2160)

2 Values based on an 80 kg individual

3
4
5
6
7
8
Volunteers will be instructed to maintain their normal physical activity during the study. However,
volunteers will be required to refrain from any additional physical activity outside of the study (resistance

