32 Hard copy data records will be stored for a minimum of three years from the time the study is completed.
33 Electronic data records will be maintained for a period of at least five years after the study has been
34 completed.
35

36 **B5.6 Managing Data and/or Human Biological Specimens for Future Research**

37 Any use of the samples outside of this defined protocol will be submitted as a protocol amendment or a
38 new protocol. Samples will be retained for future analyses once the protocol is closed if the subject
39 provided permission in the informed consent document.
40

41 **B5.8 Statistical Analysis**

42 **B5.8.1 Sample Size Estimation**

43 Statistical power and sample size were determined using the minimum fold change required for a
44 physiologically relevant difference in microRNA expression. Variance (standard deviation) was based
45 on recent publications assessing change in microRNA expression in skeletal muscle (18, 50, 51) and
46 circulating (34, 35, 52) in response to an acute bout of exercise. Using this information the sample
47 size necessary to determine statistical significance between intervention arms, with a mean fold
48

1 change of 1.5 ± 1 is 9 per group, with an alpha of 0.05 and 80% power. In the present study, 12
2 volunteers will be studied in a repeated measures crossover design to account for potential greater
3 inter-individual variability.
4

5 **B5.8.2 Data analysis**

7 Statistical analyses will be conducted using either SPSS (IBM Corp. Armonk, NY), SAS 9.3 (SAS
8 Institute Inc., Carey, NC), or equivalent. Common descriptive statistics will be used to describe
9 volunteer characteristics. Shapiro-Wilk tests will be used to determine normality of data. Mixed
10 model repeated measures ANOVA will be performed to determine main effects of time (baseline,
11 immediately, 3-hr, and 24-hr post glycogen depletion), carbohydrate intake ($6.0 \text{ g} \cdot \text{kg}^{-1} \cdot \text{d}^{-1}$ versus $1.5 \text{ g} \cdot \text{kg}^{-1} \cdot \text{d}^{-1}$) and time-by-carbohydrate interactions for skeletal muscle and circulating microRNA, mRNA
12 expression, and markers of nutritional status. If interactions are significant, Bonferroni correction will
13 be used to examine these relationships. Correlation coefficients and multiple regression analysis will
14 be used to evaluate relationships between study outcome measures. The alpha level will be adjusted

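### No period term and no stated balance of orders: a shift between the two visits, if there is one, would cost power in between-visit comparisons or, at an unequal split, move the estimate

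*Combined protocol and SAP*

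**What the plan says.** - **Allocation.** B5.3, Diet Intervention: "In this cross-over study the order of carbohydrate intake amount will be randomized to avoid order bias". The text states no ratio, block size or list method.
- **Accrual.** B5.2.2: "All screening will stop once complete data has been collected on 12 volunteers". This implies that people who do not finish are replaced, but not which order a replacement receives.
- **Model.** B5.8.2 plans a mixed model: "model repeated measures ANOVA will be performed to determine main effects of time (baseline", then "immediately, 3-hr, and 24-hr post glycogen depletion), carbohydrate intake", and their interaction. Time here means time within a visit. Period, visit and sequence are not listed. The model is named for muscle and circulating microRNA, mRNA and nutritional markers.
- **Day-2-only outcomes.** Resting respiratory quotient and exogenous carbohydrate oxidation are measured only on the second day of each visit. B5.8.2 names neither in its ANOVA. Exogenous oxidation carries Objective 2 (B4): "Determine how initiation of exercise with adequate or low glycogen stores effects exogenous" carbohydrate efficiency.
- **Gap between visits.** B5.3, Study Design: "Following a minimum 7-d washout period volunteers will return to the laboratory to complete the second arm of the investigation". No maximum is stated.

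**The concern.** Each person is measured in two visits, so the carbohydrate contrast is also a contrast between visits. Randomising the order stops this from favouring one condition on average. It does not remove a visit effect from the one trial that is run, and the stated model has nothing that would estimate it.

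The visits do differ in what precedes them. Under the Glycogen Depletion Protocol, volunteers "complete four glycogen depletion protocols, two 48-hrs before testing and two testing days". After the practice sessions, one depletion ride therefore comes before the visit-1 test day. Three depletion rides, one 80-minute ride and five biopsies come before the visit-2 test day. That makes a shift possible; it does not show one.

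Objective 2 has most at stake. Exogenous oxidation has no pre-treatment value in the same visit against which a shift could cancel.

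**Working it through.** **Inputs**
- From B5.2.2 and B5.8.1: 12 completers; fold change 1.5, SD 1; alpha 0.05; 80% power; 9 per group. Sidedness is not stated; two-sided is assumed.
- Not in the documents, so assumed: a shift s (visit 2 minus visit 1) of 0, 0.25, 0.5 or 1.0 SD of the within-person difference.
- SD of differences, σ: either 1 (the stated SD read as within-person) or 1.414, from √[2(1-ρ)] with SD 1 per condition and within-person correlation ρ = 0.

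**1. The plan's own figure.** A two-sided two-sample t-test with difference 1.5 and SD 1 has power 79.7% at 8 per group and 84.8% at 9. The stated 9 reproduces. It is a two-group calculation and does not bear on period.

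**2. Movement of the estimate.** Let n1 people take carbohydrate in visit 2 and n2 in visit 1, with true effect δ. Their differences (carbohydrate minus control) centre on δ+s and δ-s. The mean over all 12 is δ + s(n1-n2)/12. The estimate therefore moves by 0 at 6/6, 0.17s at 7/5, 0.33s at 8/4 and 0.50s at 9/3.

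**3. Error without period.** The expected variance of the differences is σ² + s² × 4·n1·n2/(12×11). At 6/6 the multiplier is 144/132 = 1.09. A shift of 0.5σ inflates the variance by 27%; a shift of 1.0σ inflates it by 109%.

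**4. Error with period.** The estimate is the average of the two sequence means, so s cancels. The standard error is (σ/2)√(1/n1+1/n2) on 10 df. At 6/6 this equals σ/√12, as without period, and only the df change (11 to 10).

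**5. Power for one value per visit, 6/6 split**

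| Effect, SD of differences | No period: s = 0 | 0.25 SD | 0.5 SD | 1.0 SD | With period |
|---|---|---|---|---|---|
| 1.5, 1 | 99.7% | 99.6% | 99.3% | 96% | 99.6% |
| 1.5, 1.414 | 92% | 90% | 87% | 68% | 91% |

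These rows are not power for the four-time-point carbohydrate main effect. The baseline and immediate biopsies precede the beverage. An effect of 1.5 at the other two points averages to (0+0+1.5+1.5)/4 = 0.75.

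**6. Unequal splits.** At 8/4, with 1.5, SD 1.414 and a shift of 0.5 SD (0.71 units), the estimate moves by 0.71/3 = 0.24. Power without period is 95% or 73% depending on direction, against 88% with it. Type I error without period, for shifts of 0.25 / 0.5 / 1.0 SD:
- 6/6: 4.4 / 3.0 / 0.6%
- 7/5: 4.6 / 3.6 / 1.5%
- 8/4: 5.2 / 5.5 / 5.1%
- 9/3: 6.2 / 9.2 / 15%

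Under simple randomisation the chances are 22.6% for 6/6, 38.7% for 7/5, 24.2% for 8/4 and 14.6% for 9/3 or worse. Averaged over all splits, type I error is 4.9 to 5.1%.

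**7. Time-by-carbohydrate.** This test compares changes within a visit. A shift equal at all four time points drops out of every such change, whatever the split. Only a shift that differs by time point reaches it.

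**The case against.** The strongest reply is that the central microRNA question is answered by the time-by-carbohydrate test, which a constant shift does not touch. That stands.

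The plan also limits a shift. It has two practice sessions, a repeated 48-hour lead-in of depletion and diet, an exercise restriction, a washout and a baseline in each visit. For exogenous oxidation, the calculation subtracts resting background enrichment, and both the relative workload and the ingestion rate are fixed. Fewer sources of shift remain than the bare design suggests. None of these measures estimates or removes what is left.

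For the day-2-only outcomes no model is stated at all, so the missing period term is part of a wider gap. B5.8.2 may also be a list of effects of interest and not a full model, since it does not list participant either. The front pages and appendices were not available for this check. These points limit how much can be read into the silence, but the remedy stays the same.

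Finally, a period term is not free. At 6/6 it gains power only once the shift exceeds about 0.18 SD (1.5 with SD 1.414) or 0.23 SD (1.5 with SD 1).

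A reader might infer that the plan is biased or inflates type I error. The documents do not support that: over simple randomisation the estimate is unbiased, and clear inflation needs both a shift and a 9/3 or worse split. Nor do they show that a shift occurs, or that the trial is underpowered because of one.

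**Conclusion.** The point holds in a limited form. The plan randomises order without stating how balance among the 12 completers is secured, and its model has no term for period. If a shift exists, the carbohydrate main effect, single-time-point contrasts and day-2-only outcomes lose power at 6/6. At an unequal split their estimates also move by (n1-n2)/12 of the shift. The time-by-carbohydrate test in its own stratum is safe from a constant shift.

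The size rests on assumed shifts. At 6/6 with one value per visit, a shift of 0.5 SD costs about 5 points of power at SD 1.414, which assumes zero within-person correlation, and under half a point at SD 1. The documents give no effect size or SD for exogenous oxidation or resting respiratory quotient, so no figure here is specific to them. This is a cheap improvement and not a flaw that undermines the trial.

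**What to change.** 1. Randomise order in blocks aimed at 6/6, and give a replacement the order of the person replaced.
2. Add period as a fixed effect, with participant as a random effect, to the cross-over models. Include the model still to be written for exogenous oxidation and resting respiratory quotient.
3. Optionally, add period-by-time as a sensitivity analysis for the time-by-carbohydrate test, since a period main effect removes only a constant shift.

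**Cost.** A randomisation list and a few lines of analysis text. Period takes one error df. With no shift, power at 6/6 falls from 91.6% to 91.1% (1.5, SD 1.414), or from 80.0% to 79.2% for an effect of 0.89 SD, chosen to give 80% power and not taken from the documents. In that second case the loss is about 2 points at 7/5, 6 at 8/4 and 13 at 9/3, so balancing the orders comes first. Period-by-time takes three df from the interaction's error, (12-1)×(4-1) = 33, leaving 30.
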